Guidelines recommend multimodal treatment combining psychosocial and educational interventions with medication. Compared with psychopharmacological treatment studies there are quite a limited number of studies on alternative treatments for children and adolescents with AD/HD²⁰. CLT's are non-invasive methods and above all NF has shown good preliminary evidence in several international studies in reducing the core symptoms of AD/HD in children, and has encouraging results in contrast to psychopharmacological treatment that the positive effect persists²¹. WMt has promising evidence of improving working memory capacity and that the good effects also can generalize into other functions but there are a clear shortage of studies comparing WMt with other active interventions and controls (Melby-Lervåg, 2012). If the results would be positive then CLT's could broaden the range of treatment for children and adolescents with AD/HD in Sweden. To date there are several different kinds of neurofeedback training options and two mainstream methods are Slow Cortical Potential training (SCPt) and frequency training (Ft) whereas the latter offers more commercially available options. For the clinical validity of this rather extensive training it is of major importance that potential improvements also last. There is a lack of follow-up studies concerning CLTs (Hodgson et al, 2012, Lofthouse et al, 2012, Melby-Lervåg et al, 2012) and the aim of this sub study is to measure long term outcome from CLT methods

Aims and objectives

Primary aim of the study is to evaluate if neurocognitive training improves core symptoms in AD/HD. Key objectives are (i) are there differences in outcome between the different neurocognitive methods, (ii) can we find predictors that differentiate learners from non-learners, (iii) are neurocognitive methods feasible in clinical settings. Additional important research questions are a) if possible improvements generalize to other settings like

school and home environment, b) does effects last six months after training, c) does the training affect the bioelectrical communication in the brain, d) are there more generalized beneficial outcomes as in perceived quality of life, stress in parents, sleep patterns.

Method/design

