The KITE study is a randomized, controlled and comparative study conducted in collaboration between Child and Adolescent Psychiatry (BUP) Division in Stockholm and Center of Neurodevelopmental Disorders at Karolinska Institutet (KIND). The study protocol was approved by Ethical Review Board in Stockholm (Dnr.2013/739-31, amendment: Dnr.2013/1729-32). The trial is registered with ClinicalTrials.gov (NCT01841151).

Eligibility and Recruitment

Participants are recruited by referrals from Child Psychiatric Clinics, ADHD-center (Habilitering & Hälsa) and children clinics (Barn- och ungdomsmedicinska mottagningar) in Stockholm County. Self-referrals are also welcome. Parents or legal guardian comes to an information meeting that is held at BUP-KIND. Before entering the study, written consent is obtained from the parent or legal guardian of the participant, and verbal assent for children under 13 or written assent for children 13 years and older. Evaluation about inclusion and exclusion criteria's is made after signed informed consent forms arrives with most recent report of neuropsychiatric evaluation confirming the ADHD diagnose.

A total of n=200 children and adolescents with AD/HD between 9-17 years of age will participate in the study alongside with treatment as usual (TAU) such as drug treatment. The duration for the participant in the study is about 30 weeks a total of; (a) baseline testing, (b) five weeks training/TAU, (c) post testing and (d) six months follow-up testing. Measurements are made with self-, parent- and teacher estimations, psychometric tests and neurophysiological measurements at measure points (a), (c) and (d). Each child and parent or guardian participate in an evaluation session to determine eligibility for the study and to establish a baseline score. To confirm AD/HD diagnosis and to ensure IQ>80 a psychiatric interview is done with parents by Kiddie Schedule for Affective Disorders and Schizophrenia for children of 6-18 years (K-SADS)²² and the participant are tested by Vocabulary and Block Design-tests from WISC IV or WAIS IV from where IQ estimate is calculated.

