We expect that participants receiving NCT will exhibit improved core ADHD symptomatology and secondary and exploratory outcomes compared with waiting list controls. Moreover, we hypothesize differing effects of Cognitive training in ADHD type of NCT (SCP, Lzs, WMt) based on the participant characteristics (e.g. genetic predisposition, age, IQ, gender, verbal skills, and comorbidity) will predict patterns of treatment effects on the various outcomes. The sample size calculation refers to the three primary outcome endpoints: change in Conners 3 total scores and subscales for parent, self-report, and blind teacher ratings between baseline and follow-up assessment, in the Intention to Treat (ITT) sample. MANOVA for repeated measures (three measurement points, withinbetween subjects' interactions, posthoc tests) will be used for the statistical analysis for the RCT study. Based on available evidence about NCT efficacy medium effects for the primary outcomes are expected. With N=200 (n=50 SCP vs. n=50 Lzs vs. n=50 WMtr vs. n=50 TAU only controls) and alpha=5%, the power (1-beta) is >99% for medium effects (G Power 3.1.7). All data provided for the participants will be included in the analyses. Data will be tested for normality and homogeneity of variance. To verify that the treatment group and control groups are comparable for continuous and categorical demographic variables at pretreatment, a series of independent-samples t-tests and chi-square tests will be conducted. As for primary outcomes, analyses for secondary outcomes will be conducted according to ITT principles. To analyse for the significance of potential factors predicting outcomes (age, IQ, language abilities, gender, comorbidity, genetic variants) in the active NCTs training groups, these are analysed using a logistic regression to explain dichotomized (by median-split) Conners 3 outcomes as the dependent variable.

Adverse events

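### The primary endpoint is change from baseline to six-month follow-up, but the planned and powered test is a three-wave group-by-time interaction that does not by itself address it

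*Combined protocol and SAP*

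**What the plan says.** In the combined protocol and SAP, the Statistical analysis section says that the sample size refers to three primary endpoints: "change in Conners 3 total scores and subscales for parent, self-report, and blind teacher ratings between baseline and follow-up assessment". The analysis sentence that follows plans "MANOVA for repeated measures (three measurement points, withinbetween subjects' interactions, posthoc tests". The power statement covers all four arms ("With N=200 (n=50 SCP vs. n=50 Lzs vs. n=50 WMtr vs. n=50 TAU only controls") and reads "alpha=5%, the power (1-beta) is >99% for medium effects (G Power 3.1.7". The effect size is described only in words: "medium effects for the primary outcomes are expected".

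Three other places bear on the time point:

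- Eligibility and Recruitment lists "c) post testing and (d) six months follow-up testing" as separate assessments, so follow-up means the six-month wave.
- Primary outcome measures names change in core symptoms on the Conners 3 by three informants and gives no time point.
- Aims and objectives places "does effects last six months after training" among the additional research questions, not in the primary aim.

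The hypothesis that opens the Statistical analysis section compares training with waiting-list controls, also without a time point.

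**The concern.** The endpoint sentence and the analysis sentence describe different null hypotheses. The endpoint concerns change from baseline to six months. The interaction null says that no arm differs from any other in change at either later wave. It can be rejected because of a difference that is present just after training and gone by six months, or because two training arms differ from each other. Neither result shows that training beats the waiting list at six months.

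The interaction test is valid for its own null. The problem is that the plan names no contrast linking it to the endpoint: no primary comparison among the four arms, no time point for the post hoc tests, and no order or error control for them. The wave and comparison that carry the conclusion could therefore be chosen after the data are seen. The power figure describes the interaction, so it does not tell the reader how well the trial can answer the endpoint question.

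**Working it through.** **Inputs from the plan.** k = 4 arms, n = 50 per arm, N = 200, m = 3 waves, alpha 0.05, stated power above 99%.

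**Assumptions, not in the plan.** Medium means f = 0.25 (omnibus) or d = 0.5 (pairwise). The correlation ρ between waves is 0.3 to 0.7, equal for all pairs (compound symmetry). There is no dropout, and one rating scale is analysed at a time.

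**1. Reproducing the stated power.** For the G*Power within-between interaction, λ = f²·N·m·ε/(1 − ρ), with (k − 1)(m − 1) = 6 and (N − k)(m − 1) = 392 degrees of freedom. With ρ = 0.5 and ε = 1, λ = 0.0625 × 200 × 3 / 0.5 = 75 and power exceeds 0.9999. With ρ = 0, λ = 37.5 and power is 0.999. So the stated figure is reproduced as the power of the 4 × 3 interaction. It is not reached under every setting: ρ = 0 with ε = 0.5 gives 0.963, and Pillai's trace with f(V) = 0.25 gives 0.978.

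**2. An effect at post-training only.** Let the three training arms differ from control by δ SD at post-training and by nothing at baseline or six months. The between-arm sum of squares at that wave is n·δ²·3/4. It is the same if only one arm has the effect. Centring over the three waves multiplies it by 2/3, so λ = 50·δ²·(3/4)·(2/3)/(1 − ρ) = 25·δ²/(1 − ρ). For δ = 0.5 this is 6.25/(1 − ρ).

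| δ | ρ | λ | Interaction power, noncentral F | Interaction rejects, simulated (Pillai) | Test of baseline-to-six-month change rejects, simulated |
|---|---|---|---|---|---|
| 0.5 | 0.3 | 8.93 | 0.577 | 0.572 | 0.051 |
| 0.5 | 0.5 | 12.5 | 0.750 | 0.741 | 0.050 |
| 0.5 | 0.7 | 20.83 | 0.946 | 0.942 | 0.048 |
| 0.3 | 0.3 | 3.21 | 0.216 | 0.211 | 0.049 |
| 0.3 | 0.5 | 4.5 | 0.298 | 0.286 | 0.050 |
| 0.3 | 0.7 | 7.5 | 0.492 | 0.480 | 0.052 |

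The simulations used 10,000 trials per row with all three training arms affected. With one arm affected, the δ = 0.5 rejection rates were 0.570, 0.742 and 0.938. With no effect at any wave the interaction rejected in 0.048 to 0.052, so its own type I error is sound.

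**3. Power for the stated endpoint.**

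- *Four-arm F test on baseline-to-six-month change*, f = 0.25 in change-SD units: λ = 0.0625 × 200 = 12.5 on 3 and 196 degrees of freedom, power 0.85.
- *One training arm versus control*, d = 0.5 in change-SD units: noncentrality 0.5 × √(50/2) = 2.5 on 98 degrees of freedom, two-sided. Power is 0.70 at 0.05, 0.53 at 0.05/3 (three contrasts) and 0.37 at 0.05/9 (three contrasts by three informants).

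**4. How far this depends on scale.** The SD of change is √(2(1 − ρ)) times the SD at one wave: 1.183, 1.000 and 0.775 for ρ = 0.3, 0.5 and 0.7. A difference of 0.5 single-wave SD is then 0.423, 0.500 and 0.645 change SD. Unadjusted power per contrast is 0.55, 0.70 and 0.89. If f = 0.25 is kept in G*Power's repeated-measures scaling with only two waves, the four-arm test stays above 0.999.

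**The case against.** The strongest reply is that repeated-measures MANOVA is a standard model, that the plan names post hoc tests, and that these could show whether a difference lies at post-training or at six months. That is correct as far as it goes. The model yields the baseline-to-follow-up contrast and need not be replaced. But the plan does not say which post hoc tests will be run or which one decides the question.

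A second reply is that only the sample-size sentence names follow-up. The hypothesis and the primary outcome section are silent on timing, and six-month persistence is listed as an additional question. The slip may therefore be in the sample-size sentence. This stands: the documents do not settle which time point was intended, only that they disagree.

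Two stronger readings are tempting but not supported. A reader might infer that the trial would be declared positive on a transient effect. The plan states no success rule and does not say that a significant interaction is the trial's conclusion. A reader might also infer a false-positive risk of about one half from two waves, three informants and three contrasts. That requires all 2 × 3 × 3 = 18 contrasts to be tested at 5% with no gate. Post hoc ordinarily means after a significant overall test. If contrasts are read only for an informant whose own interaction is significant, the simulated error falls to 0.11–0.13.

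**Conclusion.** The mismatch is in the text: the stated endpoint is baseline-to-six-month change, and the planned and powered test is a three-wave interaction whose rejection does not by itself establish that endpoint or superiority over the waiting list. Under the stated assumptions, a 0.5 SD effect confined to post-training makes the interaction significant in about 57% to 94% of trials, against about 5% for the test of the endpoint. The exact rates depend on the assumed effect and correlation, but the interaction rate exceeded the endpoint rate at every value tried. The six degrees of freedom hold for one scale at a time; a MANOVA taken jointly over informants would have more.

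The power conclusion is less firm, because the plan gives no number for a medium effect. At d = 0.5 in change-SD units, power is about 70% per contrast, or 53% with Bonferroni over three. Other scalings give higher or lower values. What can be said is that the figure above 99% belongs to the interaction and should not be read as the power of a training-versus-control contrast at six months.

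**What to change.** - Name one primary time point, and use it in the primary outcome section, the sample-size sentence and the analysis sentence. As the sample-size sentence stands, that is baseline to six-month follow-up. If post-training is meant, reword that sentence.
- Make the three training-versus-control contrasts in change to that time point, taken from the same repeated-measures model, the primary test.
- State a multiplicity rule covering the three contrasts and the three informants.
- Report the other wave as secondary and the three-wave interaction as supportive.
- Restate the power for the primary contrast, with a numerical effect size, its scale, the assumed wave correlation and the adjusted alpha.

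No new data, visits or model are needed. The costs are a less favourable stated power under the pairwise assumptions above, and an effect seen only at the other time point could no longer be claimed as the primary result.

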**A Comparative Randomized Controlled Pragmatic Trial of
Neurofeedback and Working Memory Training for Children with
Attention-Deficit/Hyperactivity Disorder: Protocol**

Abstract

Today, the treatment for children and adolescents with Attention Deficit/Hyperactivity Disorder (ADHD) is predominantly pharmacological. However, not all individuals respond to medication or experience side effects. In addition, the compliance and treatment fidelity to medication is sometimes limited, why effective non-pharmacological treatment options are desirable. Neurocognitive training (NCT) methods such neurofeedback (NF) and working memory (WMt) have shown efficacy to treat the primary symptoms of ADHD in non-blinded trials. Still, larger, comparative and blinded pragmatic randomized trials are needed to ensure their efficacy and effectiveness, and to identify an optimal training rationale. Furthermore, little is known about predictors of treatment response to NCTs, such as genetic variants. In this article we present the protocol of a randomized controlled pragmatic trial. Three NCT methods, namely two NF variants, Slow Cortical Potential training (SCP), and Live Z-Score training (LZS), as well as Working Memory Training (WMt) are evaluated against each other and a waiting list control/treatment as usual only group. In a clinical outpatient setting, N = 200 children and adolescents with ADHD aged 9-17 years and common comorbidities are randomized to one of the treatment groups or the inactive control group (n=50/group). The treatment groups (SCP/LZS/WMt) receive a total of 25 highly frequent training sessions (5/week for 5 weeks). A comprehensive assessment comprising ADHD core symptoms, psychopathology, neuropsychology, neurophysiology, quality of life and health related measures are collected pre and post treatment as well as at a 6-month follow-up. Primary outcomes are blinded teacher and unblinded parent ratings as well as self-ratings on the Conners 3 for ADHD. We expect that participants receiving NCT will exhibit improved core ADHD symptomatology compared to waiting list controls. Moreover, we hypothesize that type of NCT (SCP, LZS, WMt) and participant characteristics, such as genetic predisposition, age, IQ, gender, verbal skills, and comorbidity predict patterns of treatment effects the various outcomes.

Key words: ADHD, ADD, comorbidity, attention, treatment, neurofeedback, working memory training, RCT, evidence-based, intervention

Study protocol

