After referral or self-referral and initial evaluation based on requisitioned report on previously made assessment to establish AD/HD diagnoses the study participants are randomized to four different groups N=50 in each. Two groups of NF (SCP and Ft), WMt group, and the fourth, control group will be measured during treatment as usual (TAU) and will be able to train with self-preferred method after the last measure point. The duration of KITE study is 36 months. After initial screening the duration for participants in the study is approximately 30 weeks a total of; (a) baseline testing, (b) 5 weeks of CLT/TAU, (c) post testing and (d) six months follow-up testing. All the participants attend the study in parallel with TAU, such as drug treatment.

Inclusion criteria

Clinical diagnosis of AD/HD according to DSM-IV-TR and the K-SADS interview, drug naive or under stable medication with stimulants or equivalent for at least 1 month.

Exclusion criteria

IQ <80 (WISC-IV or WAIS-IV), clinically unstable psychiatric condition such as suffering from acute depression, bipolar disorder, severe obsessive compulsive disorder, clinically judged severe self-harming behavior, severe somatic (neurological) disease, or has a very limited knowledge of the Swedish language.

Interventions

Subjects randomized to the training groups, i.e. NF1, NF2 and WMt, comes to the clinic five times per week for five weeks, 25 sessions in total. Each session lasts about 50 minutes.

Two NF methods

NF 1: Slow cortical potential (SCP)

SCP is slower bioelectrical activity in the brain, it is a form of event related potentials (ERPs) and locked in time. It is related to phasic regulation of cortical excitability and apical dendrites of pyramidal cells are believed to be the source of the activity. SCP is characterized of negative and positive shifts lasting from 350(?) milliseconds to several seconds. The negative shift is believed to reflect brain state of allocating attentional resources and increased cortical excitability, and positive shifts reflects inhibition, reduced excitability. In this

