KITE study use a computerized software program for working memory training called Memory Quest Flex (www.flexprogram.org). Every session consists of ten different modules with eight (for younger children) or 10 (from 12 years old) different exercises in each. The different exercises stresses on either visual or auditory working memory, and the difficulty level adjusts automatically as a response to individual performance. Various kinds of positive rewards, e.g. oral and collect objects, is provided by the program. After follow-up measure participants in the WMt group are offered NF2 training in the same way as NF2 group are training.

Control

For those randomized to control group are measures collected at the same time points as for the active groups. After final data collection participants in the control group are offered NF training same as the active NF groups have obtained.

Measures

Participants using methylphenidate has a 48 hours wash-out period before measurement.

Primary outcome measures

The primary outcomes for KITE study is changes in AD/HD core symptoms measured by self-, parents- and teacher estimates by full-length Conners 3²³ forms. Conners 3 is a well-studied rating scale aimed to capture manifestations of the behavioural symptoms in AD/HD. It consists of three questionnaires (child, parent and teacher) for children between 6-17 years old.

Secondary outcome measures

Rating scales

*Behavior Rating Inventory of Executive Function (BRIEF)*²⁴ is used for parents and teachers to fill to identify dysexecutive functioning and possible improvements with neurocognitive training. It is an [86-item questionnaire](#).

KIDSCREEN-27^{25,26}; is a self-report questionnaire consisting of 27 items applicable to children between 8-18 years about perceived quality of life (QoL). Items are scored on a five-point scale; higher scores indicate better experienced QoL. The KIDSCREEN-27 has been shown to have robust psychometric properties²⁷.

*The Swedish Parenthood Stress Questionnaire (SPSQ)*²⁸ is developed from Parenting Stress Index (PSI)²⁹ and consists of 35 questions divided into five domains. The aim is to detect perceived stress related to parenthood.

*Diet and exercise questionnaire*³⁰; Swedish National Food Administration's published diet and exercise questionnaire for adults has been slightly adjusted to suit children, and parents fills it at the first measure point.

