Flankers test which is a kind of reaction time task and where the subject has to respond as quickly as possible, while avoiding errors. The participants are required to indicate the direction of a central target in an array of three stimuli. *Continuous performance test, CPT-OX* consists of 400 letters presented briefly (150ms) every 1,65 s in a pseudorandom sequence at the centre of a computer monitor. Letter "O" is the cue and initiate 40 cue-target i.e. 'O' followed by letter 'X' (go condition) or 40 cued non-target (O followed by different letter than X, no-go condition).

Randomization

Random list of numbers. The date when consent form has arrived.

Statistical analysis

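### The plan promises ITT with all data included, but the named repeated-measures MANOVA drops incomplete cases by default and no missing-data method is given

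*Combined protocol and SAP*

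**What the plan says.** In the Statistical analysis section, the three primary endpoints (parent, self and teacher Conners 3 ratings, change from baseline to follow-up) are to be assessed "in the Intention to Treat (ITT) sample". The same section says "All data provided for the participants will be included in the analyses" and applies ITT principles to the secondary outcomes. The method for the trial is given as "MANOVA for repeated measures (three measurement points", with group-by-time interactions and post hoc tests. It is not stated whether the three informants are modelled together or separately.

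The section gives N = 200 (50 per arm), alpha 5% and power above 99% for medium effects. There is no dropout allowance. Nowhere does the protocol define the ITT set, give an expected missing rate, or state how missing ratings are handled.

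Two other parts bear on the point:

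- **Raters and incentives.** The Abstract states: "Primary outcomes are blinded teacher and unblinded parent ratings as well as self-ratings". The section on working memory training says: "After follow-up measure participants in the WMt group are offered NF2 training". The control group is also offered training after the last measurement. No such offer is stated for the two neurofeedback arms.
- **Timing of baseline.** Under Eligibility and Recruitment, each child and parent "participate in an evaluation session to determine eligibility for the study and to establish a baseline score", while a later paragraph reads "initial evaluation based on requisitioned report on previously made assessment to establish AD/HD diagnoses the study participants are randomized to four different groups". The Randomization section says only: "Random list of numbers. The date when consent form has arrived". Whether baseline ratings come before allocation is known is therefore unclear.

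**The concern.** Repeated-measures MANOVA needs a full outcome vector for each child. Take a child with baseline and post-training teacher forms but no six-month teacher form. By default that child leaves the whole teacher analysis, including the post-training comparison, although the data were provided. If the informants are modelled jointly, one missing form out of nine removes the child from everything.

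The primary result could then rest on fewer children than were randomised, with less precision. The treatment of missing ratings would also be settled after data collection. Return of follow-up forms might differ by arm, since some families have further training to wait for and others do not. That last point is only a possibility; the protocol does not show it.

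**Working it through.** **1. The plan's own figure.** For the group-by-time test with 4 groups, 3 times, N = 200 and alpha 5%, "medium" is taken as f = 0.25 (assumed, since the protocol gives no number). The repeated-measures ANOVA routine uses a noncentral F with noncentrality f² × N × 3/(1 − ρ). It gives 99.9% at ρ = 0 and above 99.99% at ρ = 0.5. The MANOVA routine (Pillai, f(V) = 0.25) gives 97.8%. So the stated figure is reproduced under the ANOVA routine and nearly so under the MANOVA routine, in both cases with all 200 children complete.

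**2. Complete cases.** The missing rate q per post-baseline form is an assumption, with baselines complete and forms missing independently. Complete cases are 200(1 − q)² per informant (2 later forms) and 200(1 − q)⁶ if joint (6 later forms).

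| q | Per informant | Joint |
|---|---|---|
| 5% | 180.5 | 147 |
| 10% | 162 | 106 |
| 15% | 144.5 | 75 |

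**3. Effect on the omnibus test.** At q = 10%, the MANOVA routine falls from 97.8% to 93.8% (N = 162) or about 77% (N = 106). The ANOVA routine with ρ = 0.5 stays above 99% even at N = 106.

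**4. Effect on a two-arm contrast.** This is the baseline-to-follow-up change, n = 50 per arm, SD 1, equal correlation ρ between times (assumed), d = 0.5. Power = Φ(0.5/√V − 1.96).

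- Complete cases: V = 2 × 2(1 − ρ)/[50(1 − q)²]. With q = 0.10 and ρ = 0.5: V = 2/40.5 = 0.0494, so 0.5/√V = 2.250 and power = Φ(0.290) = 61.4%.
- Mixed model: V = 2c′I⁻¹c with c = (−1, 0, 1). Here I is 50 times the sum, over missing patterns, of pattern probability times the inverse covariance of the observed times. At q = 0.10 the pattern probabilities are 0.81 (all three), 0.09 (no follow-up), 0.09 (no post) and 0.01 (baseline only). V = 0.0430 and power = 67.4%.

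| q | ρ | V, complete cases | V, mixed model | Variance cut | Power |
|---|---|---|---|---|---|
| 5% | 0.5 | 0.0443 | 0.0414 | 6.6% | 66% → 69% |
| 10% | 0.5 | 0.0494 | 0.0430 | 12.9% | 61% → 67% |
| 10% | 0.7 | 0.0296 | 0.0259 | 12.5% | 83% → 87% |
| 15% | 0.5 | 0.0554 | 0.0448 | 19.1% | 57% → 66% |

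With full data the same contrast has 70.5% power at ρ = 0.5. A simulation at q = 10% (6000 runs) gave variances of 0.0510 and 0.0439 at ρ = 0.5, and 0.0298 and 0.0257 at ρ = 0.7, in line with the formulas.

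**5. Dropout only.** Suppose 5% are lost by post-training and a larger share by follow-up. MANOVA then uses only the children who reach follow-up, at both times.

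| Lost by follow-up | ρ | Contrast | V, complete cases | V, mixed model | Variance cut | Power |
|---|---|---|---|---|---|---|
| 20% | 0.5 | follow-up | 0.0500 | 0.0468 | 6.3% | 61% → 64% |
| 20% | 0.5 | post | 0.0500 | 0.0416 | 16.8% | 61% → 69% |
| 10% | 0.7 | follow-up | 0.0267 | 0.0261 | 2.3% | 86% → 87% |
| 10% | 0.7 | post | 0.0267 | 0.0251 | 6.0% | 86% → 88% |

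**6. Bias.** None is demonstrated. A simulation in which dropout in one arm depended on the post-training score showed almost none in the complete-case estimate. Its correlations (0.6 between post and each other time) made the change score uncorrelated with the post score, so it neither rules bias in nor out.

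**7. Baseline constraint, a separate matter.** If baseline means could be constrained equal across arms, the 10%-missing mixed-model variances would be 0.0330 (ρ = 0.5) and 0.0223 (ρ = 0.7), with power 79% and 92%. This is legitimate only if baseline ratings precede knowledge of allocation.

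**The case against.** The strongest reply is that this is an omission and not a contradiction. The plan never adopts listwise deletion, and its promise to include all data can be read as an intent to use incomplete cases. Multiple imputation followed by MANOVA would honour it. That is fair as far as it goes: replacing MANOVA is one remedy, not the only one. But the intent needs a step that the plan does not state.

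On size, several points stand:

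- The omnibus test in the plan loses little or nothing under the ANOVA routine, and the figures above concern a two-arm contrast. If the three training arms are pooled against control (150 vs 50, an assumption), 10% missing at ρ = 0.5 gives about 79% against 84%.
- Most of the gain comes from not discarding usable pairs. A change score on all available baseline and follow-up pairs gives V = 2/45 = 0.0444 and 66.0% power. The mixed model adds about 1.4 points to that (67.4%).
- Independent missingness is the more favourable scenario at follow-up, the endpoint used for sizing. Dropout only gives about 3 points at most there.
- Most of the gain from the baseline constraint has nothing to do with missing data. Baseline adjustment on complete cases alone gives about 74% at 10% missing, ρ = 0.5.
- Per-informant models leave multiplicity over three informants and their subscales unresolved.

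None of this supplies the missing rule.

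**Conclusion.** The concern holds. The named method, with default handling, does not deliver the promised analysis population, and nothing in the protocol fills the gap. This should be fixed, but it does not invalidate the design.

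The cost in power is modest and conditional. For a two-arm contrast with d = 0.5 and ρ = 0.5, it is about 3, 6 and 9 points at 5%, 10% and 15% independent missingness. Under dropout only, it is at most about 3 points at follow-up and 8 at post-training. All missing rates, correlations and the value of d are assumptions. The larger complete-case losses (down to 106 or 75 of 200) arise only if the informants are modelled jointly. The stated omnibus power is not challenged for complete data. What weighs most is the unkept inclusion promise and a missing-data rule left open until the data are in.

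**What to change.** - For each informant, replace the MANOVA with a linear mixed model for repeated measures: arm by time, unstructured covariance, REML. Fit it to all randomised children with any rating and keep baseline in the outcome vector, so that children with only a baseline form are retained. Report training versus control and between-arm contrasts at post-training and at follow-up.
- If MANOVA is kept, prespecify multiple imputation and state the imputation model.
- Define the ITT set, and add a sensitivity analysis for data missing not at random.
- State when baseline ratings are collected relative to disclosure of allocation. Adjust for baseline, or constrain baseline means to be equal, only if ratings are confirmed to come first. Otherwise leave baseline unconstrained as a repeated measure.

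The cost is analysis wording and a little more analysis work on data already planned; there are no extra visits or participants. The power statement should be restated to match the new model, and multiplicity across informants and subscales still needs its own rule. The mixed model relies on data missing at random, hence the sensitivity analysis. The baseline constraint risks bias if parents or children rate baseline after learning the allocation, so it stays conditional.
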